#### Methodology:

This is an open-label, extension trial designed to evaluate safety of additional 40 to 52 weeks of TNX-102 SL 5.6 mg taken daily at bedtime for the treatment of PTSD. There are two possible "tracks" patients can use to enroll into this study:

Track A: patients that complete the double-blind lead-in HONOR study and complete *or are active (at the time of study discontinuation) in the* 12-week open-label extension study, P303, and received active drug in the 12-week double-blind lead-in study, P301/HONOR.

Track B: patients that are currently enrolled in the double-blind lead-in P301/HONOR study that has been discontinued due to results of an interim analysis *or are active (at the time of study discontinuation) in the* 12-week open-label extension study, P303, and received placebo in the 12-week double-blind lead-in study, P301/HONOR.

The study will consist of 5 or 6 in-clinic study visits, including Baseline Visit 1 (Day 0, which is anticipated to be the same visit as the last visit of the 12-week open-label extension study P303 for Track A patients), followed by in-clinic visits after 7, 16, 28 and 40 weeks of open-label treatment. Patients who are active in the 12-week double-blind lead-in study (P301/HONOR) at the time of enrollment to P306 will also have a 2-week phone check-in visit. All Track B patients will have 52 weeks of open-label treatment and a Visit 7. For patients enrolled from the discontinued double-blind lead-in study, P301/HONOR, the P306 Baseline Visit will occur in lieu of an early termination visit.

Patient safety parameters recorded at the final visit in the double-blind lead-in HONOR study (which is the baseline visit in the 12-week open-label extension study P303) can also be used as the baseline safety values for the P306 extension study for Track A patients. Patients will attend clinic visits at 7-, 9-, and 12-week intervals as indicated in the study visit schedule. Eligible patients who provide written informed consent will be provided with a supply of TNX-102 SL 2.8 mg tablets sufficient for

dosing until their next scheduled in-clinic study visit. At each clinic visit, patients will return their TNX-102 SL medication and will receive sufficient supplies to last them until the next scheduled visit. Patients will also have the option to have blood drawn for pharmacogenomic testing.

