3. OVERALL STUDY DESIGN AND PLAN

This is a 40 to 52-week, multicenter, open-label extension study designed to establish long-term safety exposure and to examine the long-term effect with daily bedtime dosing of TNX-102 SL 5.6 mg (2 x 2.8 mg tablets) in patients with PTSD. This study will be conducted at approximately 35 sites in the United States (US).

Patients who have either: (a) completed the double-blind lead-in study (P301/HONOR study), and completed or are active (at the time of study discontinuation) in the 12-week open-label extension study, P303; or (b) are enrolled in the double-blind lead-in study (P301/HONOR study) that has been discontinued due to results of an interim analysis, will be eligible. For Track A patients, this extension study consists of 5 in-clinic visits, including the Screening/Baseline visit and visits after 7, 16, 28, and 40 weeks of treatment (Visits 3-6). There will also be a telephone visit after 2 weeks of treatment (Visit 2) for patients enrolling from the double-blind lead-in study, P301/HONOR. The total treatment duration of this study will be 40 weeks for patients enrolled under Track A criteria, and 52 weeks for patients enrolled under Track B criteria. Therefore, the maximum total duration of continuous treatment with TNX-102 SL could be approximately 64 weeks for those patients assigned to TNX-102 SL in the lead-in HONOR study who then also completed the 12-week open-label extension study P303. For patients enrolling from the open-label extension study, P303 (Track A), there is no need to repeat assessments at Visit 1 for this study, if the patient enrolls and initiates study treatment within fourteen days of completing the 12-week open-label extension study P303. For patients who are active in the double-blind lead-in study, P301/HONOR (Track B), all Baseline procedures and assessments will be completed at Visit 1.

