9.1.1 Efficacy Analysis Model

A Mixed Model Repeated Measures (MMRM) analysis will be performed for the change from baseline in separate, independent models for each endpoint. The model will include all participants in the safety population, and the dependent variable will be the observed change from baseline the outcome of interest at each post-randomization visit. Covariates in the model will include the fixed categorical effects of treatment group exposure, site, sex, visit and treatment group by visit interaction, as well as the continuous fixed covariates of baseline score and baseline score by visit interaction. An unstructured covariance matrix will be used to model the within-subject variance-covariance errors. The Kenward-Roger approximation will be used to estimate the denominator degrees of freedom. Should the unstructured model fail to converge, an autoregressive AR(1) covariance structure will be attempted, then finally compound symmetric should AR(1) not converge.

The least squares means and 95% confidence intervals (CIs) will be calculated for the treatment difference between the subjects that received TNX-102 SL in a prior study and those that did not.

These endpoints to be analyzed with this model will include:

- CGI-I score.
- Change from baseline in SDS total.
- Change from baseline in participants' quality of sleep using the PROMIS Sleep Disturbance scale.
- Change from baseline in the disruption of work/school activities assessed using the SDS.
- Change from baseline in disruption of social life/ leisure activities assessed using the SDS.
- Change from baseline in the disruption of family life/home responsibilities assessed using the SDS.
- Change from baseline in BDI-II score.

The model will be changed to include the corresponding baseline value of each the endpoints. To estimate the difference between the treatment arms in CGI-I score (which does not have baseline assessments), the same method will be used, however, with the observed baseline response and associated interactions removed from the list of covariates. All visits will be included in the analysis. P-values from these comparisons will be considered nominal.

Protocol: TNX-CY-P306 Page 20 of 36

Final v1.0

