For each outcome, descriptive statistics (mean, SD, median, minimum and maximum) will be reported as well as LS means, standard error (SE) and p-values comparing the arms at each visit. In addition, for the SDS, the frequency of participants not working or attending school due to reasons unrelated to PTSD will be reported overall and within each visit.

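### The SAP 9.1.1 repeated-measures model compares lead-in groups at every visit with no term for entry route, so the contrasts may be confounded with route by an amount the documents do not let one fix.

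*SAP*

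**What the plan says.** **Model.** SAP 9.1.1 lists the categorical terms as "fixed categorical effects of treatment group exposure, site, sex, visit and treatment group by visit interaction". The baseline value of the outcome also enters, alone and crossed with visit. For CGI-I the same model is used "with the observed baseline response and associated interactions removed from the list of covariates". There is no term for track or entry route.

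**Visits and contrasts.** SAP 9.1.1 adds "All visits will be included in the analysis" and promises "LS means, standard error (SE) and p-values comparing the arms at each visit". Week 52 is not set apart, although SAP 2.2.1 marks its Week 52 PCL-S endpoints as Track B only.

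**Who has Week 52.** SAP 3 gives 40 weeks to Track A and "52 weeks for patients enrolled under Track B criteria".

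**Tracks are defined twice.**
- The Protocol Synopsis (Methodology) places in Track A those who came through P303 "and received active drug in the 12-week double-blind lead-in study, P301/HONOR". Track B holds direct P301 entrants, with no arm stated for them, plus patients active in P303 who had placebo in the lead-in. Protocol 12.2 agrees on that last group.
- SAP 3 attaches the label Track A to P303 entrants and Track B to direct P301 entrants, and does not mention arm.

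**Groups are defined twice.**
- SAP 3.2 says treatment group means the arm randomised in the lead-in study.
- SAP 9.1.1 and 9.1.2 contrast subjects who received TNX-102 SL in a prior study with those who did not. P303 was open-label TNX-102 SL.

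**Baseline.** SAP 7.1 takes the last value before the first P306 dose. Under Protocol 9.1.2 this is normally the P303 final visit for P303 entrants, and Visit 1 for direct entrants.

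**The concern.** Route affects what change from baseline means. A P303 entrant's baseline follows a period on open-label drug. A direct entrant from the placebo arm has a baseline that precedes any active drug. CGI-I has the same difficulty, because it is rated against the start of P306 and its model has no baseline term to absorb part of the difference.

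If the two groups hold different mixes of route, a group contrast carries part of any difference between routes. At Week 52 there is a second mechanism. Track A values are absent by design, and the model fills the gap from earlier visits under missing-at-random, without conditioning on the variables that create the gap.

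At stake are the least-squares mean differences and nominal p-values for CGI-I, SDS total and items, PROMIS Sleep Disturbance and BDI-II. A reader of the study report would take them as the lasting effect of having had active drug in the lead-in.

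**Working it through.** **1. Who is observed at Week 52**

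| Tracks | Groups | Active or exposed group | Comparator |
|---|---|---|---|
| Protocol Synopsis | Randomised arm (SAP 3.2) | Direct P301 only | Direct P301 plus P303-active |
| Protocol Synopsis | Any prior TNX-102 SL (SAP 9.1.1) | Direct P301 active arm plus P303-active with lead-in placebo | Direct P301 placebo arm only |
| SAP 3 | Either | Direct P301 only | Direct P301 only |

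The stated maximum of about 64 weeks (12 + 12 + 40) fits both track definitions. It excludes only a 52-week track for active-arm P303 completers (12 + 12 + 52 = 76).

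**2. Inputs**

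The documents give up to 200 patients (Protocol 6.2) and no split by arm, route or track. The following are assumptions: arms 1:1; P303 share s in each arm 0.3 to 0.7; share f of placebo P303 patients still active at discontinuation 0.2 to 0.8; within-patient correlation ρ 0.3 to 0.7, compound symmetric; true group effect zero; no site, sex or baseline terms. Each was varied in turn around s = f = ρ = 0.5. Results are in units of the route effect δ (P303 minus direct).

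The Synopsis gives placebo P303 completers no track. Reading L leaves them out. Reading C puts them in Track A, because inclusion criterion 1 (Protocol 7.2) admits P303 completers of either arm.

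**3. Weeks 7 to 40, constant δ: difference in P303 share**

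Let p = sf/(sf + 1 − s), the P303 share of the placebo arm at Week 52 under the protocol's tracks.

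- Randomised arm, L: s − p. At the centre, 0.5 − 0.25/0.75 = 0.17.
- Randomised arm, C or SAP 3 tracks: s − s = 0. With unequal shares it is the difference between them.
- Any prior drug, C or SAP 3 tracks: 2s/(1 + s) = 1/1.5 = 0.67.
- Any prior drug, L: (s + sf)/(1 + sf) = 0.75/1.25 = 0.60.

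**4. Week 52**

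The difference in observed means is −p by randomised arm and +p by any prior drug under the protocol's tracks (0.33 at the centre). It is 0 under SAP 3 tracks.

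The least-squares mean for a group is its observed Week 52 mean plus b × (earlier-visit mean of all its patients − earlier-visit mean of those seen at Week 52), with b = 4ρ/(1 + 3ρ) = 2/2.5 = 0.8. Randomised arm, L: active 0 + 0.8 × 0.5 = 0.40, placebo 0.33, difference +0.07. If the route effect instead grows linearly to δ at Week 52, its mean over Weeks 7, 16, 28 and 40 is 0.4375δ. Active is then 0.8 × 0.5 × 0.4375 = 0.175, placebo 0.33, difference −0.16.

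**5. Ranges over the assumptions (units of δ)**

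| Groups | Tracks | Weeks 7–40, constant | Week 52 observed | Week 52 LS, constant | Week 52 LS, growing |
|---|---|---|---|---|---|
| Randomised | Protocol, L | +0.06 to +0.33 | −0.17 to −0.54 | −0.04 to +0.23 | −0.29 to +0.01 |
| Randomised | Protocol, C | 0 | −0.17 to −0.54 | −0.03 to −0.12 | −0.11 to −0.35 |
| Randomised | SAP 3 | 0 | 0 | 0 | 0 |
| Any prior drug | Protocol, L | +0.39 to +0.78 | +0.17 to +0.54 | +0.35 to +0.73 | +0.25 to +0.62 |
| Any prior drug | Protocol, C | +0.46 to +0.82 | +0.17 to +0.54 | +0.40 to +0.77 | +0.28 to +0.64 |
| Any prior drug | SAP 3 | +0.46 to +0.82 | 0 | +0.37 to +0.66 | +0.16 to +0.29 |

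**6. Effect of adding route**

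Route plus route-by-visit brings every entry under the protocol's tracks to 0, provided the route effect is the same in both groups. A route main effect alone does so only if the effect is constant. With a growing effect it leaves −0.30 to +0.25δ at Week 52. Under SAP 3 tracks no P303 entrant is seen at Week 52, so that route-by-visit term cannot be estimated (design rank 14 of 15).

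**The case against.** The strongest reply is that the documents contain a reading with no confounding. Take SAP 3's tracks and SAP 3.2's randomised groups: observed Week 52 data then come from one route, and with equal P303 shares in the two arms the spurious difference is zero at every visit. That is correct. But it needs SAP 3's track labels over the Synopsis, SAP 3.2's group over the wording of 9.1.1, and equal P303 shares, and the documents secure none of these.

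Second, under the 9.1.1 wording route is partly what defines the groups, so adjusting for it changes the question: only direct entrants then inform the contrast. This also stands, and it is why the group definition has to be settled before a route term is added.

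Third, baseline and baseline-by-visit terms absorb part of any route difference. They do, by an unknown amount, but not for CGI-I, which SAP 7.2 lists first among outcomes set out in approximate order of importance.

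Fourth, little rests on these contrasts. Safety is primary, Protocol 12.2 expects minimal efficacy conclusions, the protocol plans descriptive efficacy summaries, and SAP 7.1.1.1 calls all p-values nominal. This limits the weight of the point. It does not remove it, because calling a p-value nominal concerns error rates, not what the estimate measures.

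**Conclusion.** The point holds in a limited form. The 9.1.1 contrasts may be confounded with entry route under the protocol's tracks, and under the any-prior-drug grouping with either set of tracks. Under the stated assumptions the spurious least-squares difference runs from about −0.35 to +0.82 of the route effect, and the route effect itself is unknown.

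A reader might infer three stronger things that the documents do not support.

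- **That Week 52 is the worst visit.** It is for observed means by randomised arm under the protocol's tracks, and for least-squares means when placebo P303 completers are in Track A. With a constant route effect, the Week 52 least-squares bias is smaller than at Week 40 under the literal Synopsis with randomised arms and under every any-prior-drug reading.
- **That lead-in arm decides entry route.** Direct P301 entry is open to either arm. Among P303 entrants it is the track, and so the presence of Week 52, that the Synopsis ties to arm.
- **That the estimates are biased by a known amount or in a known direction.** There are no counts by route and arm, and the sign at Week 52 changes with the group definition.

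The consequence is confined to secondary efficacy estimates. The primary safety objective is untouched.

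**What to change.** 1. State one group definition for all of SAP 9. The randomised lead-in arm, already in SAP 3.2, is the natural choice. Align the wording of 9.1.1 and 9.1.2 with it.
2. Reconcile the track definitions in the Protocol Synopsis and SAP 3, including where placebo P303 completers belong, so that it is clear who is expected at Week 52.
3. Add entry route and route-by-visit as fixed effects to every 9.1.1 model, for visits through Week 40. Show means by arm and route at these visits, because the adjustment assumes the same route effect in both arms.
4. Report the Week 52 between-arm contrast only among direct P301 entrants. This removes the route mix under either track definition and needs no Week 52 route-by-visit term. Show other Week 52 data descriptively, by route within Track B.
5. Tabulate patients by arm, route and track, so that readers can judge how far the mix differs.

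The cost is a few degrees of freedom and a smaller sample for the Week 52 contrast. Route is already known for every patient, so no new data are needed. At Week 52 under the protocol's tracks no active-arm P303 entrant is observed, so an equal route effect across arms cannot be checked there. This is a further reason for the restriction in step 4.

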9.1.2 Categorical outcomes

The proportion of responders (participants with a CGI-I score of "much improved" or "very much improved") over time will be reported with the number and percentage of participants in each group (participants that received TNX-102 SL in a prior study and those that did not). Participants with missing data will be analyzed as though they are non-responders. A difference in proportions Z-test and the corresponding two-sided 95% CIs will also be reported. Two-sided p-values for the test of no difference between the groups will be provided.

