## 9.5. Visit 7 (Week 52)

Track B patients only: Visit 7 is to be conducted after 52 weeks ( $\pm 7$  days) of treatment in the extension study. At this visit, the patient will return all remaining study drug and the following assessments and procedures are to be completed in the following general order:

Collect returned study medication from patient and perform drug accountability

- Assess study drug compliance
- Assess for occurrence of AEs
- Assess for changes in concomitant medications
- Obtain vital signs including weight
- Draw blood for clinical laboratory tests
- For women of child-bearing potential, conduct urine pregnancy test
- Inspect the oral cavity and document findings, if any
- Have the patient complete the PCL-S
- Have the patient complete the PROMIS-Sleep Disturbance Scale and SDS
- Have the patient complete the BDI-II
- Conduct the C-SSRS after reviewing the results of the BDI-II
- Conduct CGI-I comparing to the P306 baseline

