2.2 Study Endpoints

2.2.1 Efficacy Endpoints

Comparisons will be made at each study week of data collection to the baseline of this study.

Efficacy endpoints include:

- Average CGI-I score (scored 1-7)
- Proportion of patients with a CGI-I score of "very much improved" or "much improved"
- Change from baseline in the SDS total score
- Change from baseline in the individual items assessed using the SDS
- Change from baseline in patients' quality of sleep using the PROMIS Sleep Disturbance scale
- Change from baseline in BDI-II score
- Change from week 28 to week 40 in PCL-S
- Change from week 28 to week 52 in PCL-S (Track B subjects only)
- Change from week 40 to week 52 in PCL-S (Track B subjects only)

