7. GENERAL ISSUES FOR STATISTICAL ANALYSIS

7.1 General Statistical Methodology

Descriptive summaries will be provided where appropriate for each of the primary and secondary variables. In general, tables will summarize data by treatment group as defined in Section 3.2 and visit.

All tables will be completed for the Safety Population unless otherwise specified.

Continuous, quantitative, variable summaries will include the number of participants (N) with non-missing values, mean, standard deviation (SD), median, minimum, and maximum.

Categorical, qualitative, variable summaries will include the frequency and percentage of participants who are in the particular category. In general, the denominator for the percentage calculation will be based upon the total number of participants in the study population for the treatment group unless otherwise specified.

Unless otherwise noted, baseline values are defined as the last non-missing measurement prior to the first dose of open-label study drug in Study TNX-CY-P306. Change from baseline will be defined as the post-baseline visit value minus the baseline value.

ET participants will only be followed if required to monitor an on-going adverse event or other condition.

Participants are not supposed to change study sites; however, should this be necessary to allow a participant to continue in the study, participants will be analyzed under the site where they were initially enrolled.

Study day after first dose is defined as assessment date – first dose date +1. Dates prior to first dose are defined as assessment date – first dose date. Note that the protocol refers to "Day 0"; for the purposes of the datasets and analyses, this would appear as day 1.

All analyses will be performed using Statistical Analysis System (SAS®) Software version 9.4 or later.

Unless otherwise noted, 95% confidence intervals will be presented for statistical tests.

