7.1.1 Adjustments for Multiplicity and Other Alpha Control

7.1.1.1 Multiplicity

No adjustments will be made from multiplicity and all p-values will be nominal.

7.1.2 Data Handling for Participants Who Discontinue Study Drug or Withdraw from the Study

Participants who withdraw/drop out from the study will have their ET visit data collected and included in the analysis based on the closest visit window (Week 7, 16, 28, 40, or 52). Visit windows will be assigned by splitting the periods between visits at the midpoint between the visits. If more than one record falls within the window, the one closest to the target date will be used in the analysis, with preference given to the scheduled visits in the case of equidistant visits.

Protocol: TNX-CY-P306 Page 15 of 36

Final v1.0

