7.2.1 Clinician Global Impression of Improvement (CGI-I)

The CGI-I will be completed by an Investigator to evaluate the participant's status since the start of the current study (P306). The CGI-I will be completed at each in-clinic visit after baseline. It will be the responsibility of the Principal Investigator or his qualified designee to assess change in the subject's overall status and answer the following question:

Since the initiation of treatment in P306, the participant is:

- 1 = Very much improved
- 2 = Much improved
- 3 = Minimally improved
- 4 =No change
- 5 = Minimally worse
- 6 = Much worse
- 7 =Very much worse

The primary analysis of CGI will treat it as a continuous variable (scored 1-7 as above). There will be an additional outcome presented where a responder on the CGI-I is defined a participant who is scored as 'Very much improved' or 'Much improved' and compared between the study arms.

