7.2.2 Sheehan Disability Scale (SDS)

The SDS scale is a self-report questionnaire that was designed to assess the participant's view of the degree to which symptoms have disrupted work/school, social life/leisure activities, and family life/home responsibilities during the previous 2 weeks (Sheehan & Sheehan, 2008). In addition, the SDS asks the participant to provide the number of days of work/school lost as well as unproductive days in the past two weeks. The SDS scale will be completed by the participant at Baseline and after 7, 16, 27, and 40 weeks, plus 52 weeks for Track B participants. A total score will be calculated summing the three individual 11-point (0-10) scales. For participants that do not respond to the work/school disruption because the participant checked the box indicating he/she has not worked or attended school for reasons unrelated to the disorder (PTSD), the total score will sum the other 2 domain questions and multiply by 1.5 (rounding up to the nearest whole number) to maintain the scale of 0-30 for the total score. Participants with missing values on the other items will be missing for the total.

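### As written, the Week 52 CGI-I responder analysis counts Track A patients, who have no Week 52 visit, as non-responders and biases the comparison against the prior-TNX-102 SL group

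*SAP*

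**What the plan says.** SAP 9.1.2 reports the number and percentage of CGI-I responders over time in two groups, patients with and without TNX-102 SL in a prior study, with a difference-in-proportions Z-test and two-sided 95% CI. Its missing-data rule carries no exception: "Participants with missing data will be analyzed as though they are non-responders".

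Four other provisions decide what that rule does at Week 52:

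- **Time points.** SAP 2.2.1 makes comparisons at every study week with data collection. SAP 7.1.2 says early-termination data are "included in the analysis based on the closest visit window (Week 7, 16, 28, 40, or 52", so Week 52 is an analysis window.
- **Denominator.** SAP 7.1 states that, in general and unless otherwise specified, "the denominator for the percentage calculation will be based upon the total number of participants in the study population for the treatment group".
- **Schedule.** Protocol 9.5: "Track B patients only: Visit 7 is to be conducted after 52 weeks". The CGI-I is among the assessments at that visit. Track A stops at Week 40 (Protocol 6.1, SAP 3).
- **CGI-I timing.** SAP 7.2.1: "The CGI-I will be completed at each in-clinic visit after baseline".

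For other instruments the SAP does limit Week 52. The PCL-S endpoint in SAP 2.2.1 reads "Change from week 28 to week 52 in PCL-S (Track B subjects only", and the SDS description in SAP 7.2.2 has "plus 52 weeks for Track B participants"; PROMIS in 7.2.3.1 is treated the same way. No such limit is attached to the CGI-I responder analysis.

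**The concern.** A patient who was never due a Week 52 rating has no Week 52 value. Under an unqualified rule that missing means non-response, with the whole group as denominator, that patient counts as a treatment failure.

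The failures do not fall evenly. SAP 3 describes the entry route as "For patients enrolling from the open-label extension study, P303 (Track A", and the Protocol synopsis also routes Track A through P303. P303 was an open-label TNX-102 SL study (its title is in SAP 14), so every Track A patient has prior exposure. The group without prior exposure consists of placebo patients who entered directly from P301, and they are all Track B.

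The Week 52 percentage, difference, CI and p-value would therefore partly measure enrolment route. Protocol 12.2 says the efficacy analyses focus on durability of response, based on the CGI-I. At the longest follow-up, an artificial drop in the longer-exposed group would read as loss of response.

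**Working it through.** The plan gives no responder rate, track split or sample-size calculation, so there is no stated figure to reproduce. The direction follows from the text. The size below is an illustration.

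**Could a Track A visit fill the Week 52 window?** Protocol Appendix 1 sets the targets at Day 280 and Day 365. The midpoint rule in SAP 7.1.2 puts the boundary at (280 + 365)/2 = Day 322.5. An on-schedule Track A final visit (Day 280 ± 7, at latest Day 287) stays in the Week 40 window.

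**Formula.** Let r be the true Week 52 response, equal in both groups, and f the share of the prior-exposure group that is Track A. The displayed rates are (1 − f) × r for prior exposure and r for no prior exposure.

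**Assumed base case.** 200 patients (the protocol's upper limit), 100 per P301 arm. Each arm is 40% direct from P301, 30% P303 completers and 30% active in P303 when it stopped. r = 50%, no dropout. Prior exposure: 100 from the active arm + 60 placebo patients who entered P303 = 160. No prior exposure: 40.

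The documents do not define Track A consistently, so three readings are shown:

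- (a) P303 completers of both arms, plus P303-active patients who had active drug in P301: 60 + 30 = 90 in Track A.
- (b) Only patients with active drug in P301, as the Protocol synopsis literally says: 60.
- (c) All P303 enrollees, as SAP 3 labels them: 120.

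Expected z for (a): the displayed rate is 70 × 0.5/160 = 0.219 against 0.500. The pooled rate is (35 + 20)/200 = 0.275. SE = √(0.275 × 0.725 × (1/160 + 1/40)) = 0.0789. z = −0.281/0.0789 = −3.56. The same steps for (b) give −0.1875/0.0843 = −2.22.

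Rejection rates come from exact binomial enumeration of the pooled two-sided Z-test at 0.05, with Track A counts fixed. There is no true difference in any row.

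| Setting | Groups | Track A | Displayed | Rejects |
|---|---|---|---|---|
| (a) r = 50% | 160 vs 40 | 90 | 22% vs 50% | 94% |
| (b) r = 50% | 160 vs 40 | 60 | 31% vs 50% | 61% |
| (c) r = 50% | 160 vs 40 | 120 | 12.5% vs 50% | >99% |
| (a) half size | 80 vs 20 | 45 | 22% vs 50% | 71% |
| (b) half size | 80 vs 20 | 30 | 31% vs 50% | 35% |
| (a) route mix 70/15/15 | 130 vs 70 | 45 | 33% vs 50% | 67% |
| (b) route mix 70/15/15 | 130 vs 70 | 30 | 38% vs 50% | 34% |
| (a) r = 30% | 160 vs 40 | 90 | 13% vs 30% | 71% |
| (b) r = 30% | 160 vs 40 | 60 | 19% vs 30% | 36% |
| f = 20%, r = 50% | 160 vs 40 | 32 | 40% vs 50% | 21% |
| f = 10%, r = 50% | 160 vs 40 | 16 | 45% vs 50% | 9% |

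The rule can also hide a real benefit. A true 60% versus 50% in favour of prior exposure disappears in the display once f = 1 − 50/60 = 16.7%.

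**Restricted to Track B.** With r = 50%, 70 vs 40 in (a) and 100 vs 40 in (b) each reject in about 5% of trials.

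**Grouping by randomized arm.** SAP 3.2 defines treatment group as the P301 arm, which is not the grouping in 9.1.2. With 100 vs 100 and r = 50%, active vs placebo shows 20% vs 35% in (a), rejecting in 69% of trials, and 20% vs 50% in (b), rejecting in over 99%. In (c) both arms show 20%: no bias in the contrast, but each rate is 20% instead of 50%.

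**The case against.** The strongest reply is that an assessment never scheduled is not missing data. SAP 3 gives Track A five in-clinic visits ending at Week 40, and SAP 7.2.1 ties the CGI-I to in-clinic visits, so a sensible programmer would leave Track A out at Week 52. The denominator rule is hedged, and SAP 15.1.2 says population sizes shown with summary statistics are the non-missing n. This shows that a benign reading exists. It does not show that the SAP adopts it. The visit count confirms that Track A has no Week 52 rating without exempting it from the rule, and the n shown beside summary statistics does not settle the denominator of a percentage in which missing values have been set to non-response.

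The second reply concerns size, and much of it stands. Route mix, response rate, a full 200 patients and no dropout are all assumed, and a small Track A share does little harm. The direction against prior exposure also depends on the 9.1.2 grouping; under SAP 3.2 with reading (c) the contrast is unbiased.

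The third reply is that little depends on this result. Protocol 12.2 expects minimal efficacy conclusions, p-values are nominal, and the responder outcome is additional to the continuous CGI-I analysis. That is correct and limits the severity. It is also fair that a Track B-only comparison still contrasts patients with different prior exposure, whose CGI-I is rated from different starting points. The restriction removes the scoring artefact and does not make the groups comparable in other respects.

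**Conclusion.** The concern holds: followed as written, the rule gives a wrong Week 52 responder result. Under the groups named in SAP 9.1.2, any Track A share above zero lowers the prior-exposure rate and leaves the other group untouched. That direction needs no assumption about the split.

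The size does. In the illustrations the false-difference rate runs from about 9% at a 10% Track A share to over 99% when all P303 enrollees are Track A, assuming equal true response and no dropout.

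Only Week 52 of the responder analysis is affected. Weeks 7 to 40 are not, nor is the MMRM in SAP 9.1.1, which uses observed data without imputation. The primary safety objective is untouched. This should be fixed before the analysis is run, but it does not threaten the study's main conclusions.

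**What to change.** Amend SAP 9.1.2 to state that:

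- the Week 52 CGI-I responder numerator, denominator, Z-test and CI use Track B patients only, as already done for the PCL-S;
- missing counts as non-response only at visits scheduled for the patient's track;
- Week 40 is the last comparison that includes all patients.

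Reconcile the group definition in SAP 3.2 (randomized P301 arm) with that in 9.1.2 (any prior TNX-102 SL), and say which one this analysis uses.

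The cost is two or three sentences and no new data. Week 52 rests on fewer patients. In illustration (a), 70 vs 40 gives a 95% CI half-width of 1.96 × √(0.25/70 + 0.25/40) = 0.194, about 19 points. If all 200 had a Week 52 rating it would be 1.96 × √(0.25/160 + 0.25/40) = 0.173, about 17 points.
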